4 STUDY DESIGN

4.1 OVERALL DESIGN

The clinical hypotheses for this study are as follows:

- SYD-101 is safe as assessed by the incidence and severity of AEs compared with Vehicle
- SYD-101 is superior to Vehicle in slowing the progression of myopia
 - For European Medicines Agency (EMA) submission, the primary assessment of myopia progression will be assessed by the mean annual progression rate of myopia
 - For US Food and Drug Administration (FDA) submission, the primary assessment of progression will be assessed by the proportion of participants with an increase in myopia >0.75 D

This is a Phase 3, multicentered, randomized, double-masked, vehicle-controlled study to assess the safety and efficacy of SYD-101 eyedrops in male and female children between 3 and 14 years of age (inclusive) with myopia of 0.50 D to 6.00 D (inclusive).

The study will have 3 treatment groups: SYD-101 0.01%, SYD-101 0.03%, and the Vehicle of SYD-101. Each night at bedtime, 1 drop of masked study drug will be instilled in each eye. See [Section 1.2](#) for the figure describing the treatment assignments.

- **Baseline Randomization.** At Baseline, participants will be randomly assigned into 1 of 3 treatment arms, with participants allocated in a 1:1:1 ratio to receive either SYD-101 0.01%, SYD-101 0.03%, or Vehicle during Part 1 (Primary Treatment Period). Allocation to the treatment groups will be stratified according to the following 2 factors: baseline SE and age (see [Section 6.3](#) for stratification details). Enrollment thresholds may be utilized to limit the number of participants in each level of demographic characteristic such as age group, baseline SE group, race, etc. These thresholds will be defined within the interactive voice response system (IVRS)/interactive web response system (IWRS) and may be modified during the course of the study.
- **Re-randomization.** At Month 36, participants will be randomly assigned to receive study treatment during Part 2 (Randomized Withdrawal Period) as follows:
 - Those initially assigned to the SYD-101 0.01% arm will be re-randomized in a 1:1 ratio to receive either masked SYD-101 0.01% or Vehicle
 - Those initially assigned to the SYD-101 0.03% arm will be re-randomized in a 1:1 ratio to receive either masked SYD-101 0.03% or Vehicle

- Those initially assigned to the Vehicle arm (not on escape medication) will be re-randomized to receive masked SYD-101 0.03%

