6.3 MEASURES TO MINIMIZE BIAS: RANDOMIZATION AND MASKING

Allocation to study treatment will occur in a double-masked manner on 2 occasions: **initial randomization** at Baseline (for Primary Treatment Period [Part 1]) and **re-randomization** at Month 36 (for Randomized Withdrawal Period [Part 2]).

For Part 1, prior to initiation of study treatment, randomization will occur by site staff via the IVRS/IWRS once it is confirmed that the participant meets the final study entry criteria (see [Sections 5.1](#) and [5.2](#)). The IVRS/IWRS will provide the participant identification number used on all study documents and will be used to manage the randomization and treatment assignment based on a stratified randomization scheme prepared by Sydnexis' designee. Initial randomization will be in a 1:1:1 ratio of SYD-101 0.01%: SYD-101 0.03%: Vehicle and stratified by baseline SE (0.50 D to 3.0 D and >3.0 D to 6.0 D) and age (3 years to <6 years, 6 years to <9 years, 9 years to <12 years, and 12 years to 14 years).

To maintain treatment masking for Part 2, sites will contact the IVRS/IWRS at Month 36 for all participants. At Month 36, participants who were initially assigned (at Baseline) to SYD-101 0.01% will be re-randomized in a 1:1 ratio to masked SYD-101 0.01% or Vehicle; participants initially assigned (at Baseline) to SYD-101 0.03% will be re-randomized in a 1:1 ratio to masked SYD-101 0.03% or Vehicle. The Re-randomization of SYD-101 participants will not be stratified. All participants who were initially assigned (at Baseline) to Vehicle will be re-randomized to masked SYD-101 0.03% at Month 36.

Sites will also contact the IVRS/IWRS at the time a participant qualifies to initiate treatment with escape medication (ie, at confirmatory visit when measurements confirm progression of myopia ≥ 2.00 D in SE from baseline) for ANY participant who has qualified for and desires to use escape medication.

Study drug will be labeled with medication kit numbers, and the IVRS/IWRS will provide each site with the specific medication kit number(s) for each randomized participant at the time of

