randomization and any required drug resupply visit. Additionally, to maintain study masking, the IVRS/IWRS will assign a new medication kit for all participants at any timepoints study treatments might switch based on study design (ie, the re-randomization at Month 36, at escape for confirmed ≥ 2.00 D progression), even if the new medication kit will be of the same treatment type of the medication kit currently assigned. Sites will dispense study drug according to the IVRS/IWRS instructions. Sites will receive the IVRS/IWRS confirmation notifications for each transaction. All notifications are to be maintained with the study source documents.

Masking of individual participant treatment assignments will be maintained throughout the study for all participants and required site staff until the database is locked for the EOS analysis at Month 48. If it is necessary for the safety and appropriate treatment of a participant, the treatment assignment can be unmasked by the site via the IVRS/IWRS. When possible, the medical monitor should be notified prior to the unmasking, and the reason for breaking the mask will be documented in the source documentation. The investigator should inform the medical monitor of the unmasking if there is no notification prior to the unmasking. The treatment assignment for the participant can be determined by designated site staff calling into the IVRS/IWRS via password-protected access. The reason for breaking the code must be recorded in the participant's source documents and electronic case report form (eCRF).

To minimize bias, results of the Month 24 analyses for EU submission will neither be made public, nor shared with study sites nor study monitors until after completion of the Month 36 analysis.

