7 STUDY DRUG DISCONTINUATION AND PARTICIPANT DISCONTINUATION OR WITHDRAWAL FROM STUDY

7.1 DISCONTINUATION OF STUDY DRUG

Discontinuation from study drug does not mean discontinuation from the study, and remaining study procedures should be completed as indicated by the study protocol. If a clinically significant finding is identified (including, but not limited to changes from baseline) after enrollment, the investigator or qualified designee will determine if any change in participant management is needed. Any new clinically relevant finding will be reported as an AE.

The data to be collected at the time of study intervention discontinuation will include the procedures as listed in the schedule of activities.

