9.4.9 EXPLORATORY ANALYSES

Data collected after Month 36 will be considered exploratory analysis and summarized separately using descriptive statistics. Participants will be grouped by treatment pathway from the start of study through the re-randomization (original SYD-101 0.01% and SYD-101 0.03% participants) and transition to active treatment (original Vehicle participants) at Month 36:

- Participants initially randomized to SYD-101 0.01% at Baseline and re-randomized to SYD-101 0.01% at Month 36
- Participants initially randomized to SYD-101 0.01% at Baseline and re-randomized to Vehicle at Month 36
- Participants initially randomized to SYD-101 0.03% at Baseline and re-randomized to SYD-101 0.03% at Month 36

- Participants initially randomized to SYD-101 0.03% at Baseline and re-randomized to Vehicle at Month 36
- Participants initially randomized to Vehicle at Baseline and re-randomized to SYD-101 0.03% at Month 36

In general, data collected after Month 36 will be summarized according to the above groupings. As applicable, the groupings above may be further refined based on receipt of escape medication between Month 24 and Month 42 (inclusive). Changes in continuous measures will be relative to the data collection at the Month 36 visit, unless otherwise specified. Adverse events will be summarized separately for those events with onset after Month 36.

To evaluate the potential rebound effect once participants discontinue SYD-101 therapy, exploratory analyses will be conducted on the set of participants initially randomized to SYD-101 (0.01% or 0.03%) at Baseline who are re-randomized to Vehicle at Month 36. The mean annual progression rate from baseline to Month 36 will be numerically compared to the mean annual progression rate from Month 36 to Month 48 within this set of participants.

Select summaries will be provided for the group of participants initially randomized to SYD-101 (0.01% or 0.03%) at Day 1 (Baseline) and re-randomized to SYD-101 at Month 36 and who remain on SYD-101 for the entire duration of the study. This will be done to characterize the safety and efficacy profile of those participants receiving up to 48 months of SYD-101 treatment.

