4.2. Randomization, Stratification, and Masking

Allocation to study treatment will occur in a double-masked manner on 2 occasions: initial randomization at Baseline (for Primary Treatment Period [Part 1]) and re randomization at Month 36 (for Randomized Withdrawal Period [Part 2]).

For Part 1, prior to initiation of study treatment, randomization will occur by site staff via the IVRS/IWRS once it is confirmed that the participant meets the final study entry criteria. The IVRS/IWRS will provide the participant identification number used on all study documents and will be used to manage the randomization and treatment assignment based on a stratified randomization scheme prepared by Sydnexis' designee. Initial randomization will be in a 1:1:1 ratio of SYD-101 0.01%: SYD-101 0.03%: Vehicle and stratified by baseline SE (0.50 D to 3.0 D and >3.0 D to 6.0 D) and age (3 years to <6 years, 6 years to <9 years, 9 years to <12 years, and 12 years to 14 years). Sites will also contact the IVRS/IWRS at the time a participant qualifies to initiate treatment with escape medication (ie, at confirmatory visit when measurements confirm progression of myopia ≥ 2.00 D in SE from baseline) for any participant who has qualified for escape medication.

For Part 2, to maintain masking, sites will contact the IVRS/IWRS at Month 36 for all participants. At Month 36, participants who were initially assigned (at Baseline) to SYD-101 0.01% (not on escape medication) will be re-randomized in a 1:1 ratio to masked SYD-101 0.01% or Vehicle; participants initially assigned (at Baseline) to SYD-101 0.03% (not on escape medication) will be re-randomized in a 1:1 ratio to masked SYD-101 0.03% or Vehicle. Re-randomization of SYD-101 participants will not be stratified. All participants who were initially assigned (at Baseline) to Vehicle (not on escape medication) will be re-randomized to masked SYD-101 0.03% at Month 36. Participants who have escaped to open label SYD-101 0.03% therapy at or prior to Month 36 will remain on escape therapy medication.

Masking of individual participant treatment assignments will be maintained throughout the study for all participants and site staff until the database is locked for the EOS analysis at Month 48.

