5.1. Disposition

Two separate disposition summaries will be provided:

A disposition of participants includes the number and percentage of participants for the following categories: participants who signed informed consent/assent, participants randomized, participants randomized by region and country, participants in the Safety analysis set, participants in the FAS, participants in PPS, participants who completed Month 24 and Month 36 visits, participants who completed the study, participants who discontinued from the study, participants who discontinued from the study treatment, and participants who received escape medication. Additional disposition summaries will be provided for subgroups such as Age, Sex, Race and Iris Color.

A separate summary will be provided for randomized withdrawal period and will contain counts and percentages of participants in the following categories:

- Those initially assigned to the SYD-101 0.01% arm (not on escape medication) will be re-randomized in a 1:1 ratio to receive either masked SYD-101 0.01% or Vehicle
- Those initially assigned to the SYD-101 0.03% arm (not on escape medication) will be re-randomized in a 1:1 ratio to receive either masked SYD-101 0.03% or Vehicle
- Those initially assigned to the Vehicle arm (not on escape medication) will be re-assigned to receive masked SYD-101 0.03%

All percentages will be based on the number of FAS participants. Disposition data will be listed as well.

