To evaluate the potential rebound effect once participants discontinue SYD-101 therapy, exploratory analyses will be conducted on the set of participants initially randomized to SYD-101 (0.01% or 0.03%) at Baseline and who are re-randomized to Vehicle at Month 36. The mean annual progression rate from baseline to Month 36 will be numerically compared to the mean annual progression rate from Month 36 to Month 48 within this set of participants. For comparison, the same summaries will be presented for participants randomized SYD-101 therapy and who are not re-randomized to Vehicle at Month 36. Summary statistics will be presented by initial randomization group.

To evaluate the potential rebound and re-treatment effect once participants discontinue SYD-101 therapy, exploratory analyses will be conducted on the set of participants initially randomized to SYD-101 (0.01% or 0.03%) at Baseline and who are re-randomized to Vehicle at Month 36. The mean annual progression rate from Baseline to Month 36 will be numerically compared to the mean annual progression rate from Month 36 to Month 48 within this set of participants to investigate rebound. For comparison, the time intervals will be summarized for participants randomized SYD-101 therapy and who are not re-randomized to Vehicle at Month 36. Additionally, these summaries will also be subset by receipt of escape medication after Month 36.

To evaluate the escape medication effect, select summaries and plots will be provided by numerically comparing the participants who never received escape medication and the participants who received escape medication at Month 24, Month 30 and Month 36 by initial randomization group. Summaries and plots will be presented from Baseline to Month 36, and will include:

- Mean change from baseline in SE
- Mean annual progression rate

- Mean change from baseline in axial length

Select summaries will be provided for the subset of participants initially randomized to SYD-101 (0.01% or 0.03%) at Day 1 (Baseline) and re-randomized to SYD-101 at Month 36 and who remain on SYD-101 for the entire duration of the study. This will be done to characterize the efficacy profile of those participants receiving up to 48 months of SYD-101 treatment. Summaries to be presented for this subset of participants includes:

- Mean change from baseline in SE
- Mean annual progression rate from baseline to Month 48
- Proportion of participants with myopic progression >0.75 D at or before Month 48

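### The SAP's rebound comparator is not the randomized counterpart of the children withdrawn to Vehicle, and neither group has to be on SYD-101 at Month 36

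*Protocol*

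**What the plan says.** **Rebound set.** Protocol 9.4.9 defines it as "participants initially randomized to SYD-101 (0.01% or 0.03%) at Baseline who are re-randomized to Vehicle at Month 36". Within it, the mean annual progression rate from Baseline to Month 36 is compared numerically with the rate from Month 36 to Month 48.

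**Comparator.** SAP 8.3 repeats that set and adds: "For comparison, the same summaries will be presented for participants randomized SYD-101 therapy and who are not re-randomized to Vehicle at Month 36". Results are shown by initial randomization group. A further paragraph adds a split by escape medication received after Month 36.

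**Who is re-randomized.** Protocol 6.3 goes by Baseline assignment: "participants who were initially assigned (at Baseline) to SYD-101 0.01% will be re-randomized in a 1:1 ratio to masked SYD-101 0.01% or Vehicle", with a parallel rule for 0.03%. The SAP exempts children on escape. Section 5.1 reads "Those initially assigned to the SYD-101 0.01% arm (not on escape medication) will be re-randomized in a 1:1 ratio", and section 4.2 reads "Participants who have escaped to open label SYD-101 0.03% therapy at or prior to Month 36 will remain on escape therapy medication". No other exemption is stated.

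**Children off drug.** Protocol 7.1 states: "Discontinuation from study drug does not mean discontinuation from the study, and remaining study procedures should be completed as indicated by the study protocol". Protocol 9.2 plans follow-up to Month 48 whether or not drug is stopped. On what happens to these children at Month 36, the wording points both ways. Protocol 4.1 says "At Month 36, participants will be randomly assigned to receive study treatment during Part 2 (Randomized Withdrawal Period) as follows", while Protocol 6.3 has the system "assign a new medication kit for all participants at any timepoints study treatments might switch based on study design".

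**Exposure.** For SYD-101 children sent to Vehicle, SAP 7.3.1 takes the re-randomization date as the last SYD-101 dose. It makes no exception for an earlier stop.

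**The concern.** A randomized withdrawal answers the rebound question through its 1:1 split: children sent to Vehicle against children kept on SYD-101. SAP 8.3 defines its comparison group by exclusion, so it gathers everyone from the SYD-101 arms who was not sent to Vehicle, including children who never entered the split. The contrast then mixes withdrawal with selection, and for some children with a change of dose.

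Separately, the summary is meant to show what happens when SYD-101 stops. A child who stopped at, say, Month 18 has off-drug time in the earlier rate and nothing to withdraw at Month 36. By contrast, the set in Protocol 9.4.9 used to describe up to 48 months of treatment does require remaining on SYD-101.

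What is at stake is how the rebound summaries and the SYD-101 exposure table are read. Rebound after higher-dose atropine is a reason the protocol gives for looking at Month 48 (Section 3).

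**Working it through.** The plan gives no figure for the rebound analysis, so there is none to reproduce. Inputs from SAP 4.1: 0.65 D/year on Vehicle, 0.325 D/year on active, SD 0.55 D, and 7% per year for dropout and treatment discontinuation combined. The active arms hold 2 × 280 = 560 children.

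**1. Membership under the current wording**

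| Status at Month 36 (SYD-101 arms) | Rebound set | SAP 8.3 comparator |
|---|---|---|
| On masked drug, sent to Vehicle | yes | no |
| On masked drug, kept on SYD-101 | no | yes |
| On open-label escape | no | yes |
| Off drug, sent to Vehicle (if re-randomized) | yes | no |
| Off drug, assigned SYD-101 (if re-randomized) | no | yes |
| Off drug, not re-randomized | no | yes |

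The escape row follows from the SAP alone and needs no assumption.

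**2. How different the escape children are.** Escape requires confirmed progression of at least 2.00 D. A child starting it at Month 36 has a Baseline-to-Month-36 rate of at least 2.00/3 = 0.667 D/year, about twice 0.325. The same bound holds for earlier starters if their myopia does not regress.

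If a share e of SYD-101 attendees is on escape, the comparator is (1 − e)/2 + e = (1 + e)/2 of attendees, so escape children make up 2e/(1 + e) of it. The documents give no e. Assuming 2%, 5% and 10% gives 3.9%, 9.5% and 18.2%. The comparator's Baseline-to-Month-36 mean is then raised by at least that share × (0.667 − 0.325), or 0.013, 0.033 and 0.062 D/year. The rebound set contains none of these children. Their rate after Month 36 cannot be sized from the documents.

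**3. Off-drug share.** Cumulative loss by Month 36 is d = 1 − 0.93³ = 0.1956. The documents do not split this between leaving the study and stopping drug, so assume a share s stays in follow-up off drug. Among Month 36 attendees, p = ds / (1 − d(1 − s)):
- s = 0: p = 0
- s = 0.25: p = 0.0489/0.8533 = 0.0573
- s = 0.5: p = 0.0978/0.9022 = 0.1084

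**4. Before/after rise if stoppers are re-randomized.** Take the stop at Month 18 (the mean is 17.3 under a constant 7% per year), so f = 18/36 = 0.5. Let r be extra rebound above the Vehicle rate. An on-drug child rises by 0.325 + r. A stopper sent to Vehicle rises by 0.65 − (0.325f + 0.65(1 − f)) = 0.325f = 0.1625, ignoring any rebound at the earlier stop. Set rise = (1 − p)(0.325 + r) + 0.1625p.

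| r (assumed) | On-drug rise | s = 0.25 | s = 0.5 |
|---|---|---|---|
| 0 | 0.325 | 0.316 (2.9% low) | 0.307 (5.4% low) |
| 0.10 | 0.425 | 0.410 (3.5% low) | 0.397 (6.7% low) |
| 0.20 | 0.525 | 0.504 (4.0% low) | 0.486 (7.5% low) |

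If no child who stops leaves the study (s = 1, p = 0.196), the r = 0 loss is 9.8%. Uniform stop times give similar results at r = 0: 2.5% low at a 5% share, 5.0% at 10%.

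**5. Difference in rises between the two groups** (s = 0.25 and 0.5, escape ignored)
- Stoppers re-randomized, those assigned SYD-101 restart it: 0.325 + r − pr. No loss at r = 0; 2.2% and 4.1% low at r = 0.20.
- Re-randomized but staying off drug in both groups: (1 − p)(0.325 + r), so 5.7% and 10.8% low.
- Not re-randomized: they form q = 2p/(1 + p) = 0.108 and 0.196 of the comparator. At r = 0 the difference is 0.325 − 0.325qf = 0.307 and 0.293, 5.4% and 9.8% low; it is 0% low if they stopped near Baseline. The comparator's Month 36–48 rate is 0.325(1 + q) = 0.360 and 0.389 instead of 0.325.

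**6. Exposure.** Month 18 is day 546 and Month 36 is day 1092 (SAP Table 4-1). A child who stopped at Month 18 and was re-randomized to Vehicle is credited with 1092 − 546 = 546 extra days. The excess is 0 if not re-randomized.

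**The case against.** The strongest reply on the comparator is that planned outputs already isolate the right children. SAP 8.3 tabulates pathway groups, including those re-randomized to the same SYD-101 dose; SAP 4 by default summarizes children under current treatment after escape; and a set staying on SYD-101 for 48 months is defined. This helps only in part. The pathway groups receive the Month 36–48 rate but not the before/after pair. The rebound summary is shown by initial randomization group, which departs from the default. Its escape split covers only escape after Month 36. SAP 8.3 also has an escape-effect summary separating children by escape start, but it ends at Month 36. The 48-month set depends on staying on drug after Month 36, so it is not a randomized counterpart either.

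On the off-drug children, the objection largely stands. Neither document says they are re-randomized, and Protocol 4.1's language of assignment to receive treatment fits them poorly. The share is assumed, zero is within its range, and Protocol Table 9-2 says most study discontinuations are logistical withdrawals of consent. Extra rebound is also assumed: Protocol 2.1.2 reports rebound after 1% atropine but none after 0.01%. The r = 0 shift of 0 to 0.018 D/year is small beside 0.55/√239 = 0.036 for a single mean rate. The standard error of a within-child change equals that only if the two rates have equal SDs and correlate at 0.5; at zero correlation it is about 0.050. Slowing with age, which the SAP introduction mentions, could move the rise by more.

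A reader might infer that the plan does dilute the rebound estimate, or that the between-group contrast must shrink. The documents support neither: the first depends on an unstated Month 36 rule, and step 5 includes cases with no loss.

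**Conclusion.** A minor point and a cheap improvement. What holds without assumption is that the SAP 8.3 comparator includes SYD-101 children on escape at Month 36, who were never part of the 1:1 split and were selected for fast progression. What holds conditionally is that, if children who stopped drug earlier are re-randomized, the before/after rise is modestly understated and exposure overstated for those sent to Vehicle. The rise is about 3% to 5% low with no extra rebound and up to 7.5% low with an assumed 0.20 D/year, given off-drug shares of 5.7% and 10.8%, a Month 18 stop and the SAP's planning rates. If they are not re-randomized, the within-set rise is untouched but they fall into the comparator.

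It would be wrong to read this as a threat to the efficacy conclusions. Data after Month 36 are exploratory and descriptive, and no test, alpha allocation, or primary or secondary endpoint is involved.

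**What to change.** 1. SAP 8.3: define the comparator as participants re-randomized to SYD-101 at Month 36.
2. Protocol 9.4.9 and SAP 8.3: keep the re-randomized grouping and add one rebound summary limited, in both groups, to participants still taking masked SYD-101 at the Month 36 visit, with status fixed before re-randomization. Report how many were already off drug.
3. SAP 7.3.1: use the actual last SYD-101 dose date when it precedes re-randomization.
4. As a clarification, state in Protocol 4.1/6.3 and SAP 4.2 whether off-drug participants are re-randomized.

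The cost is a few sentences and one descriptive table, using treatment status that SAP 7.3.1 already collects at each visit. The added table is slightly smaller. Ignoring escape and combining doses, the Vehicle set loses about 14 of 239 children at s = 0.25 (560 × 0.8533/2 = 239; × 0.0573 = 14) or 27 of 253 at s = 0.5. The re-randomized rebound set loses no one.
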